8.5 DERIVED AND TRANSFORMED DATA

8.5.1 Baseline Values

In general, Baseline is defined as the last value for an assessment prior to randomization. This value may be obtained at either the Screening or the Baseline visit, depending upon the visit schedule.

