3.3 CLINICAL ASSESSMENTS

3.3.1 *Efficacy*

3.3.1.1 *Assessment of Clinical Worsening*

Efficacy will be assessed by a composite primary endpoint of clinical worsening assessed at Day 14 or hospital discharge, whichever comes first, as defined by one of the following events:

- Death
- Initiation of ECMO per institutional policies
- Need for additional treatment (initiation of additional targeted pulmonary vasodilator therapy for PPHN)

Clinical worsening will be evaluated from Baseline (initiation of study drug) to the time of discontinuation of study drug, discharge from the hospital, or at the conclusion of Day 14, whichever comes first. Events occurring after the first 14 days of treatment will not count towards the primary endpoint.

3.3.1.1.1 *Need for Additional Treatment*

The following criteria should be met prior to initiation of additional targeted pulmonary vasodilator therapy for PPHN (all criteria required):

- OI measurement >20
- In the clinical judgment of the Investigator, subject requires addition of another targeted pulmonary vasodilator therapy (e.g., PDE-5i, ERA, alternate prostanoid [epoprostenol, iloprost], L-citrulline) due to worsening of clinical status or unsatisfactory clinical response
- Subject has received study drug for at least 24 hours and reached a minimum dose of 10ng/kg/min, or is unable to tolerate further increases (e.g., due to systemic hypotension); **OR**
 - If less than 24 hours, subject has two consecutive OI measurements >30 separated by at least one hour **OR** two consecutive arterial lactate levels of $\geq 4\text{mmol/L}$ separated by at least one hour

If an additional pulmonary vasodilator therapy is added after Day 14, the subject will not meet the primary endpoint definition of clinical worsening.

3.3.1.1.2 *Extracorporeal Mechanical Oxygenation (ECMO)*

ECMO will be initiated per institutional policy. Any subject who initiates on ECMO during the first 14 days of the study will meet the definition of clinical worsening. The initiation of ECMO after Day 14 will not be considered a clinical worsening event for the purposes of the primary endpoint of the study.

3.3.1.1.3 *Death*

Any subject who dies within the first 14 days of the study will meet the definition of clinical worsening. Deaths that occur after Day 14 will not be considered a clinical worsening event for the purposes of the primary endpoint of the study.

All deaths will be reported as a serious adverse event (SAE) (Section 9).

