10.3.3 Safety Analyses

Safety of study drug in neonates will be evaluated by combined assessments of AEs, clinical laboratory parameters, vitals, and physical examination findings. All subjects who receive study drug will be included in the safety population. Statistical summaries of safety data will be

descriptive and exploratory in nature, focusing on the incidence of adverse experiences. The safety data collected in this study will be presented in listings and summary tables.

Treatment-emergent changes in vital signs, incidence of treatment-emergent AEs, and treatment-emergent changes in clinical laboratory parameters will be evaluated.

All AEs will be coded according to the Medical Dictionary for Regulatory Activities (MedDRA) dictionary. The incidence of AEs within each treatment group will be presented in summary tables overall, and by system organ class and preferred term.

Vital sign and clinical laboratory data collected prior to initiation of study drug will serve as Baseline values for evaluation of data collected during the treatment period. Summary statistics will be calculated for measured values at each time point assessed, as well as change from baseline values within each cohort.

No inferential statistical analyses are planned for safety data.

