8.3.2 Missing Data Handling for Secondary Efficacy Endpoints

For any continuous secondary endpoint, missing values will be imputed using last observation carried forward (LOCF). If an assessment is missing at Baseline, change from Baseline will not be calculated and the subject will not be included in the analyses of this assessment.

Time to event will be derived as detailed in Section 8.5.3.

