8.5.3 Time to Event and Censor Status

Time to event and censor status will be calculated based on the rules in Table 8-1 for time to clinical worsening, time to initiation of ECMO, and time to discontinuation of iNO.

Table 8-1 Time to Event and Censor Status Rules

Parameter	Scenario	Formula	Censor Status
Time to Clinical Worsening (days)	Subject with clinical worsening or subject died between Baseline and Day 14	= minimum of (Worsening date, death date) - Randomization date	0 (event)
	Subject without clinical worsening between Baseline and Day 14	= minimum of (Last assessment date - Randomization date, 14)	1 (censored)
Time to initiation of ECMO (days)	Subject initiated ECMO between Baseline and Day 14	= Initiation date - Randomization date	0 (event)
	Subject did not initiate ECMO between Baseline and Day 14	= minimum of (Last assessment date - Randomization date, 14)	1 (censored)
Time to discontinuation of iNO (days)	Subject discontinued iNO between Baseline and Day 14	= iNO discontinuation date - Randomization date	0 (event)
	Subject did not discontinue iNO between Baseline and Day 14	= minimum of (Last assessment date - Randomization date, 14)	1 (censored)

ECMO, extracorporeal mechanical oxygenation; iNO, inhaled nitric oxide

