8.6 ASSESSMENT WINDOWS

For some assessments, target study day and time have been specified in the protocol. These scheduled assessments, as recorded on the eCRFs, and the corresponding target days and times and study days and time intervals are specified in [Table 8-2](#).

Table 8-2 Assessment Windows for Scheduled Assessments

Visit	Target Study Day/Time	Study Day/Time Interval
Echocardiograms:		
Day 7	Day 7	2 ≤ Study Day ≤ 9
Day 14	Day 14	10 ≤ Study Day
Vital signs, OI, FiO₂, Blood Gas/Lactate:		
Hour 6	Day 1/6 hours	1 ≤ Study Day 1, Hour 6 ≤ 9
Hour 12	Day 1/12 hours	10 ≤ Study Day 1, Hour 12 ≤ 15
Hour 18	Day 1/18 hours	16 ≤ Study Day 1, Hour 18 ≤ 21
Hour 24	Day 1/24 hours	22 ≤ Study Day 1, Hour 24 ≤ 27
Hour 30	Day 2/6 hours	28 ≤ Study Day 2, Hour 6 ≤ 33

Visit	Target Study Day/Time	Study Day/Time Interval
Hour 36	Day 2/12 hours	34 ≤ Study Day 2, Hour 12 ≤ 39
Hour 42	Day 2/18 hours	40 ≤ Study Day 2, Hour 18 ≤ 45
Hour 48	Day 2/24 hours	46 ≤ Study Day 2, Hour 24 ≤ 51
Hour 54	Day 3/6 hours	52 ≤ Study Day 3, Hour 6 ≤ 57
Hour 60	Day 3/12 hours	58 ≤ Study Day 3, Hour 12 ≤ 63
Hour 66	Day 3/18 hours	64 ≤ Study Day 3, Hour 18 ≤ 69
Hour 72	Day 3/24 hours	70 ≤ Study Day 3, Hour 24
PK Assessments		
After 24 hours of study drug dosing	Day 1	24 hours ± 12 hours

Abbreviations: FiO₂, fraction of inspired oxygen; OI, oxygenation index; PK, pharmacokinetic(s)

Note: Study Day = (Assessment Date) - (First Dosing Date) +1

For assessments that are not listed in [Table 8-2](#), the nominal assessment name recorded in the eCRF will be used.

Multiple Evaluations Within the Same Analysis Window

After all the observations have been slotted based on the specifications above, if there are multiple valid observations for an assessment within an assigned analysis visit window, only 1 of these observations will be used for summary statistics and analyses. The observation to be used is determined using the following hierarchy (in decreasing order):

- The observation closest to the target study day and time
- The later observation if 2 observations are equally close to the target study day and time

For missing values where the LOCF algorithm is applied, it is always the last valid observation on treatment carried forward, even though this might not be the observation obtained by the above hierarchy and used in the summaries by visit window.

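### Baseline and time zero are set at randomisation in some places and at first dose in others, and separately SAP Table 8-1 times hour-scale events by subtracting calendar dates

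*SAP*

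**What the plan says.** The SAP uses randomisation as its anchor in two places. In 8.5.1, "Baseline is defined as the last value for an assessment prior to randomization". In Table 8-1, time to clinical worsening is "minimum of (Worsening date, death date) - Randomization date", time to ECMO is "Initiation date - Randomization date" and time to stopping iNO is "iNO discontinuation date - Randomization date". All three are in days, with censored times capped at 14.

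Other places start at first dose. Protocol 3.3.1.1: "Clinical worsening will be evaluated from Baseline (initiation of study drug"). Protocol 10.3.3: "Vital sign and clinical laboratory data collected prior to initiation of study drug will serve as Baseline values". Footnote a of protocol Table 3-1 puts Hour 0 at the start of study drug. The SAP note under Table 8-2 reads "Study Day = (Assessment Date) - (First Dosing Date) +1", and the SAP's ITT set admits only infants who received a dose.

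The protocol is not uniform either. Section 4.3.1.2 counts the 14 days for an added vasodilator from randomisation, and footnote a of Table 3-1 ties reuse of Screening values to the 3 hours around randomisation.

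For a missing Baseline, SAP 8.3.2 says: "If an assessment is missing at Baseline, change from Baseline will not be calculated and the subject will not be included in the analyses".

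**The concern.** There are two separate faults.

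The first is the origin. SAP 8.5.1 and protocol 10.3.3 give different answers for a sample drawn after randomisation but before the infusion starts. Under the protocol a laboratory value drawn then is Baseline; under the SAP it is not. Such a value precedes treatment in a blinded trial, so there is no statistical reason to refuse it. The 14-day window has the same ambiguity.

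The second is resolution. Failure can come within hours: protocol 3.3.1.1.1 allows the vasodilator criterion to be met before 24 hours, on two high OI or lactate readings at least one hour apart. Subtracting dates gives every same-date event time 0 and can reverse the order of two infants. At stake are the time-to-event curves and their medians, and the NT-proBNP change analysis for any infant sampled late. If the origin stays open until after unblinding, it also becomes a choice made with the data in view.

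**Working it through.** **1. Origins side by side**

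| Quantity | Place | Counts from |
|---|---|---|
| Baseline value | SAP 8.5.1 | randomisation |
| Baseline, vital signs and laboratory | Protocol 10.3.3 | first dose |
| Start of worsening window | Protocol 3.3.1.1 | first dose |
| Hour 0 | Protocol Table 3-1, footnote a | first dose |
| 14 days, added vasodilator | Protocol 4.3.1.2 | randomisation |
| Time to event, cap of 14 | SAP Table 8-1 | randomisation date |
| Study Day | SAP Table 8-2 note | first dosing date = Day 1 |

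**2. Which values are exposed.** Protocol 7.2 completes Baseline assessments, then randomises, then doses as soon as possible, with no stated maximum gap. OI, blood gas, FiO2 and SpO2 are also Screening items, so a value before randomisation exists. Clinical laboratories and NT-proBNP are scheduled at Baseline only and do not carry the asterisk that lets a Screening value stand in. A late draw of these two has no fallback. NT-proBNP is a secondary endpoint, so 8.3.2 removes the infant. For laboratory data the result is a conflict with protocol 10.3.3. The documents do not say how many such draws to expect.

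**3. Date arithmetic.** Randomised at 23:00 with ECMO at 01:00 the next day: 2 hours elapsed, Table 8-1 gives 1 day. Randomised at 01:00 with ECMO at 21:00 the same day: 20 hours elapsed, Table 8-1 gives 0. The order is reversed. Using the first-dose date as origin would not cure this.

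**4. Share of events at time 0.** The plan gives no figure, so event-time shapes are assumed. If the origin's clock time is uniform over the day, an event T days later falls on the same date with probability max(0, 1 − T). For log-normal T with median m days and log-SD 0.9, the average is Φ(a) − m·exp(0.405)·Φ(a − 0.9), where a = −ln(m)/0.9:

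- m = 0.75: 0.625 − 1.124 × 0.281 = 0.31
- m = 1.5: 0.326 − 2.249 × 0.088 = 0.13
- m = 3: 0.111 − 4.498 × 0.017 = 0.03

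In simulation (800 trials per setting), 38%, 23% and 13% of event pairs were tied or reversed for these three medians.

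A second set used Weibull times with the plan's 33 per group and 60% versus 30% by Day 14, and a gap from randomisation to dose of up to 1 or 6 hours:

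- constant hazard (about 10% of events in the first 24 hours): 4–5% at time 0
- about 34% in the first 24 hours: 20–23%
- about 48% in the first 24 hours: 31–36%

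**5. Effect on the log-rank test.** The plan's sample size reproduces: 33 per group gives 80.1% power one-sided, and the same formula gives 69.6% two-sided, which is why two-sided log-rank power sits near 70%. Over 1,500 runs per Weibull setting, power was 68–72% with exact hours from first dose and 69–71% with Table 8-1 dates. The largest difference was 2 points, within simulation error. In the log-normal set, significance differed between the two timings in about 1–3% of trials.

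**6. Day 14.** By the Study Day formula, Day 14 is first-dose date + 13, while Table 8-1 caps at 14. With randomisation and dose on one date, a Day 14 event has time 13. With dosing on the next date it has time 14, equal to the cap. The chance of different dates is gap/24: 1/24 = 4%, 3/24 = 12.5%, 6/24 = 25%. In the Weibull runs, an exact 336-hour cut and a Study Day 14 cut classified on average 0.24 to 0.74 of 66 infants differently.

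**7. Table 8-2 labels.** Twenty-four hours after first dose is always the next date: 1 + 1 = Study Day 2. Seventy-two hours gives 3 + 1 = Study Day 4, as footnote b of protocol Table 3-1 says. Table 8-2 labels these Day 1 and Day 3.

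**The case against.** Randomisation is a standard time origin in a blinded trial analysed as randomised, and the protocol itself uses it in 4.3.1.2. This stands: nothing in the documents makes first dose the only correct origin for time to event, and the defensible request is for one stated origin.

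A reader might infer that pre-dose values are discarded in general. Protocol 7.2 does not support that. No assessment is scheduled between randomisation and first dose, and infants enrolled as planned keep their baselines under either definition. Section 8.5.1 is also worded as a general rule, though it names no exception.

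A reader might also infer that calendar-day timing follows from choosing randomisation. It does not; it comes from the subtraction of dates.

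Finally, a reader might infer that Table 8-2 misfiles data. With dosing uniform over the day, (6 + 12 + 18 + 24)/(4 × 24) = 62.5% of on-time six-hourly values carry a later Study Day than their label. But the interval limits run continuously in elapsed hours (28–33 for the second day's first window, for example), so this counts labels; no misallocated value is shown.

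The affected efficacy endpoints are secondary, exploratory, and tested only if the primary succeeds (SAP 8.4). The shortest assumed median is aggressive, because the vasodilator criterion usually requires 24 hours on study drug and infants about to start ECMO are excluded. All of this limits the size of the point. It does not remove the conflict between SAP 8.5.1 and protocol 10.3.3, or the reversed event order.

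**Conclusion.** The point holds in two limited parts. The origin conflict is plain on the page, but its practical loss is confined to laboratory and NT-proBNP samples first drawn between randomisation and first dose, in a number the documents do not give. The date subtraction is a real error of resolution. About 3% to 36% of events would get time 0, depending on how early events fall, and some pairs of infants would be ranked in the wrong order. That range rests on assumed event-time shapes and a uniform clock time.

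The damage is to the Kaplan-Meier curves, the medians and their interpretation. A reader might infer a material loss of power or a bias toward one arm. The simulations show no material power loss, and nothing in the documents points to a bias. The chi-square test on the primary endpoint is touched only through infants whose event falls at the Day 14 boundary, on average fewer than one in 66 under the shapes tried. The change is worth making because it is cheap and should be settled before unblinding.

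**What to change.** 1. SAP 8.5.1: define Baseline as the last value before the start of the first infusion, by date and time.
2. SAP Table 8-1: time = (event date-time − origin date-time)/24 hours. State one origin, first dose or randomisation, and use it for all three endpoints, the censoring cap and the Day 14 cut. Fall back on the date alone only where no clock time was recorded. Reconcile protocol 3.3.1.1 and 4.3.1.2 with that choice.
3. SAP Table 8-2: label the hourly windows by elapsed hours from first dose and remove the Day labels from those rows, which conflict with the Study Day note and with footnote b of protocol Table 3-1. This corrects labels and moves no data.

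The cost is SAP wording and minor programming. The protocol synopsis already has the time of ECMO initiation and time on iNO recorded. What remains is to confirm that the eCRF holds a clock time for the start of an added vasodilator; if it does not, the date-only fallback applies to that component.

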8.5.2 Change from Baseline Values

Change from Baseline for an assessment is defined as the difference between the observed value and its associated Baseline value.

8.5.3 Time to Event and Censor Status

Time to event and censor status will be calculated based on the rules in Table 8-1 for time to clinical worsening, time to initiation of ECMO, and time to discontinuation of iNO.

Table 8-1 Time to Event and Censor Status Rules

Parameter	Scenario	Formula	Censor Status
Time to Clinical Worsening (days)	Subject with clinical worsening or subject died between Baseline and Day 14	= minimum of (Worsening date, death date) - Randomization date	0 (event)
	Subject without clinical worsening between Baseline and Day 14	= minimum of (Last assessment date - Randomization date, 14)	1 (censored)
Time to initiation of ECMO (days)	Subject initiated ECMO between Baseline and Day 14	= Initiation date - Randomization date	0 (event)
	Subject did not initiate ECMO between Baseline and Day 14	= minimum of (Last assessment date - Randomization date, 14)	1 (censored)
Time to discontinuation of iNO (days)	Subject discontinued iNO between Baseline and Day 14	= iNO discontinuation date - Randomization date	0 (event)
	Subject did not discontinue iNO between Baseline and Day 14	= minimum of (Last assessment date - Randomization date, 14)	1 (censored)

ECMO, extracorporeal mechanical oxygenation; iNO, inhaled nitric oxide

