5 SAMPLE SIZE CONSIDERATIONS

Based on the systematic review of use of nitric oxide for respiratory failure in infants by Finer and Barrington (2006), 57.9% (194/335) subjects in the control group had an outcome of death or requirement for ECMO (Finer 2006). In this study, assuming 60% of subjects in the placebo group and 30% of subjects in the Remodulin group with an outcome of death, requirement for ECMO, or need for additional PH therapy, we calculated that 66 subjects (33 subjects per treatment group) will have at least 80% power to show a significant difference in favor of Remodulin at alpha level 0.05 (1-sided test). Approximately 70 subjects are planned to be

randomized (1:1) to either receive treatment with Remodulin or placebo in addition to the standard of care.

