8 GENERAL CONSIDERATIONS FOR DATA ANALYSES

All the data collected in the electronic Case Report Form (eCRF) will be listed. In general, listings will be sorted by treatment group, subject number, and scheduled assessment (if applicable). Listings will include assessment date, assessment time (if available), study day, and all relevant data collected in the eCRFs. For data collected on a fixed schedule, the assessment identifier or the nominal time point will also be included on the listing. Repeat or redundant observations within an assessment window and observations that do not fall within any predefined assessment window (and will, therefore, be excluded from summaries) will be flagged in these listings. Subjects who are not to be included in the analysis population (eg, Safety population, Per Protocol population) will be flagged.

In general, the data will be summarized by scheduled assessment (if applicable) within each treatment group. For continuous variables, summary statistics will include the mean, standard deviation, median, minimum, and maximum. For summaries of non-normal data, interquartile range (lower quartile, upper quartile) may also be included. Minimums and maximums will be expressed using the level of precision in which the variable was collected. All other statistics will be rounded, using an additional decimal place than was collected. For discrete variables, summaries will include the frequency and percentage in each category. Percentages will be rounded to 1 decimal place. For all inferential analyses and descriptive comparisons, p-values will be rounded to 4 decimal places. Values less than 0.0001 will be denoted as <0.0001, and values greater than 0.9999 will be denoted as >0.9999 whenever practical. Categories of discrete variables will be ordered and labelled as they appear in the eCRF, and all categories represented on the eCRF will be included in summaries, even when they do not apply to any subjects in the study.

Unless otherwise specified, all statistical tests will be 2-sided at alpha level 0.05. All statistical calculations will be completed using the SAS® Version 9.4 or above.

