10.2.5 Time to Clinical Worsening

Data on the clinical worsening assessment page of the eCRF will be used to determine clinical worsening status. Clinical worsening events including the date (study day) of the event and details of the clinical worsening event will be listed. The time to clinical worsening will be calculated according to the rules specified in [Table 8-1](#).

Time to clinical worsening will be summarized by treatment group using product-limit estimates calculated by the Kaplan-Meier method, and displayed graphically as Kaplan-Meier curves. A tabular summary of this analysis will include the number of subjects at risk (sample size), estimated median duration, and a 95% confidence interval for the median duration for each treatment group. The log-rank test will be used to calculate the p-value for treatment differences.

The SAS Procedure LIFETEST will be used. The pseudo SAS statements are listed below:

```
proc lifetest;
  time TimeToWorsening*Censor_Status(1);
  strata Treatment;
run;
```

In addition, the Cox proportional hazards model will be fit to obtain the hazard ratio. The model will include treatment as an explanatory variable. The SAS procedure PHREG will be used.

The pseudo SAS statements are listed below:

```
proc phreg;
  Model TimeToWorsening*Censor_Status(1) = treatment
    / risklimits alpha=0.05 ties=efron;
run;
```

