10.2.6 Time to Initiation of ECMO

Time to initiation of ECMO will be analyzed as described in Section 10.2.5.

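### Time to ECMO censors infants who die without ECMO, so the comparison can favour the arm with more such deaths even when death-or-ECMO is equal

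*SAP*

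**What the plan says.** SAP Table 8-1 (Section 8.5.3) gives time to ECMO two scenarios. An ECMO start by Day 14 is an event. The other scenario is "Subject did not initiate ECMO between Baseline and Day 14", censored at "minimum of (Last assessment date - Randomization date, 14" days. There is no separate rule for death. The clinical-worsening row of the same table does have one: "Subject with clinical worsening or subject died between Baseline and Day 14" is an event.

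On method, SAP 10.2.6 says "Time to initiation of ECMO will be analyzed as described in Section 10.2.5". Section 10.2.5 gives Kaplan-Meier estimates, then "The log-rank test will be used to calculate the p-value for treatment differences", and adds that "the Cox proportional hazards model will be fit to obtain the hazard ratio". Protocol 10.3.2 also names Kaplan-Meier and log-rank for this endpoint. Neither document mentions competing risks, cumulative incidence, or an analysis of death or ECMO without additional therapy.

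Two other provisions matter. SAP 8 states "Unless otherwise specified, all statistical tests will be 2-sided at alpha level 0.05". SAP 8.4 tests secondary endpoints only if the primary is significant, and calls those comparisons exploratory.

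**The concern.** An infant who dies without ECMO can no longer receive it. Censoring at the last assessment removes the infant from the risk set, and Kaplan-Meier then assumes the same later ECMO risk as in survivors. The curve therefore estimates ECMO incidence in a population in which nobody dies first, and it lies above the proportion of infants who actually start ECMO.

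The between-arm comparison is the larger issue. Death and ECMO are alternative failures of the same sick infant, and the documents themselves pair them: the planning rate of 57.9% is the proportion for which "subjects in the control group had an outcome of death or requirement for ECMO". If one arm has more deaths before ECMO, it has fewer ECMO starts, and the log-rank and hazard ratio look better for that arm although no infant has done better. Protocol 1.1 cites PPHN mortality of 4-33%, so deaths without ECMO cannot be assumed negligible. At stake is the reading of one secondary hazard ratio and p-value.

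**Working it through.** **Plan's own figures.** The documents state no size or power for time to ECMO. The control rate checks: 194/335 = 57.9%. The arm size also checks for the primary endpoint: with 60% vs 30%, pooled rate 45%, one-sided 0.05 and 80% power, n = [1.645·√(2·0.45·0.55) + 0.842·√(0.6·0.4 + 0.3·0.7)]² / 0.30² = (1.157 + 0.565)² / 0.09 ≈ 33 per arm. I use 33 per arm below.

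**Step 1: a constructed example.** Each arm has 33 infants and 20 death-or-ECMO events on identical days between Day 1 and Day 12. Only the split between death without ECMO and ECMO differs. These splits are assumed. The log-rank statistic is (O − E)²/V, and the hazard ratio is approximated by exp[(O − E)/V], with O and E the observed and expected ECMO starts on drug.

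| Deaths without ECMO, placebo vs drug | O | E | HR | p (ECMO) | p (death or ECMO) |
|---|---|---|---|---|---|
| 2 vs 2 | 18 | 18.0 | 1.00 | 1.00 | 1.00 |
| 2 vs 6 | 14 | 16.0 | 0.77 | 0.47 | 1.00 |
| 2 vs 8 | 12 | 15.0 | 0.66 | 0.26 | 1.00 |
| 2 vs 10 | 10 | 14.0 | 0.55 | 0.12 | 1.00 |
| 2 vs 12 | 8 | 13.0 | 0.45 | 0.045 | 1.00 |

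The hazard ratio moves with modest imbalances. Significance needs about 10 extra deaths without ECMO in one arm.

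**Step 2: Kaplan-Meier against actual incidence.** In the 2 vs 12 case, one minus Kaplan-Meier is 56.2% on placebo and 30.6% on drug. The actual proportions starting ECMO are 18/33 = 54.5% and 8/33 = 24.2%. The overstatement is 1.7 and 6.4 points. Cumulative incidence of ECMO alone therefore widens the apparent difference (30.3 points against 25.6). It becomes interpretable only beside death without ECMO: 2/33 = 6.1% and 12/33 = 36.4%.

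**Step 3: simulation without the gate.** Assumptions: 33 per arm; placebo 40% ECMO plus 5% death without ECMO; 45% in total in both arms; exponential times truncated at Day 14, mean parameter 3 days for ECMO and 1 day for death; two-sided 0.05, counting only results in favour of the drug.

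| Drug arm: ECMO + death without ECMO | Log-rank on ECMO favours drug | Log-rank on ECMO or death favours drug |
|---|---|---|
| 40% + 5% | about 2% | about 2% |
| 35% + 10% | about 4% | about 2% |
| 25% + 20% | about 15% | about 2% |
| 20% + 25% | about 25% | about 2% |

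Repeat runs move the last two ECMO figures by one or two points. With later deaths (mean 3 days, ECMO mean 3 or 1 days) they are about 18-22% and 31-36%, and the ECMO-or-death figures are 2-4%.

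**Step 4: adding the SAP 8.4 gate.** The primary chi-square on death, ECMO or additional therapy must first be significant.

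- No additional therapy in either arm: the 20% and 25% death cases give about 3-4%.
- Equal additional-therapy rates: about 2-3%.
- Additional therapy in 0.15/0.55 = 27% of otherwise event-free placebo infants (taking placebo to the planned 60%) and in none on drug: about 12-16%; a repeat run gave 12.5% and 17.4%.

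The gate can open this way. With 15/33 death-or-ECMO in each arm, 8 more placebo infants with additional therapy only gives 23 vs 15: chi-square = 66·(23·18 − 15·10)² / (33·33·38·28) = 3.97, p = 0.046.

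**The case against.** The strongest objection is that the plan already limits the damage. Secondary tests are gated and exploratory. Death is an event in the primary endpoint and in time to clinical worsening. Deaths are summarised by arm (Table 14.3.1.4), clinical-worsening events are listed with details, and infants with a contraindication to ECMO are excluded (Protocol 4.2). A four- to five-fold excess of deaths would be noticed. All of this stands, and it makes the ungated 15% and 25% an upper view of the risk under this SAP. The exclusion applies only at entry, however, and the listed deaths summary is not specified as restricted to Day 14 or to deaths without ECMO.

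A reader might infer more than the documents support:

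- **That the rule is biased towards treprostinil.** It favours whichever arm has more deaths before ECMO, and the effect vanishes with an equal split.
- **That the simulated rates are inflated type I error.** In the unequal scenarios the ECMO-specific hazard really is lower on drug. The log-rank is a valid cause-specific comparison; the fault lies in reading it as clinical benefit.
- **That dead infants count as ECMO-free to Day 14.** They leave the risk set at the last assessment.
- **That no planned table combines death and ECMO.** Tables 14.2.1.1 and 14.2.2.6 do, but only together with additional therapy.
- **That the endpoint must be replaced.** Protocol 2.2 names time to initiation of ECMO, and the problem can be met by additions.

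**Conclusion.** The concern holds as a problem of interpretation for one gated, exploratory secondary endpoint. The plan has no rule for death as a competing event, so its Kaplan-Meier curve overstates ECMO incidence and its hazard ratio can move well away from 1 with identical death-or-ECMO. How far depends on the death/ECMO split, its timing and the additional-therapy rates, none of which the documents give. A small imbalance (10% vs 5% deaths without ECMO) barely raises the chance of a significant result. A large one raises it materially, and after the gate mainly if additional therapy also differs strongly. The change is worth making before unblinding.

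**What to change.** - **SAP Table 8-1 and 10.2.6:** keep time to initiation of ECMO as the protocol names it, but define death without ECMO as a competing event. Replace the Kaplan-Meier display (Figure 14.2.3) with cumulative incidence of ECMO and of death before ECMO, side by side by arm. Label any retained log-rank and hazard ratio for ECMO as cause-specific.
- **Add time to ECMO or death through Day 14**, with log-rank and hazard ratio, to be read alongside any ECMO result. A competing-risks test on ECMO alone would not serve, because replacing ECMO by death still lowers ECMO incidence.
- **Add one Day-14 table by arm:** death, ECMO, additional therapy, and death or ECMO.
- **Record the departure** from the Kaplan-Meier wording in Protocol 10.3.2.

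The cost is one extra derivation, one table and one more exploratory test. The data are already collected.
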